**Machine learning to predict lymph node metastasis
in T1 esophageal squamous cell carcinoma:
A multicenter study**

July 15, 2021

Statistical Analysis Plan

Predictor characteristics

Machine-learning models were developed using data on patients' age and sex, depth of tumor invasion, tumor size, tumor location, macroscopic tumor type, lymph vascular invasion, and histologic grade. Most of our data were structured as binary features except for age and tumor size. Location was three categorical variables. Age and tumor size were normalized to be in a range [0, 1]. The Fisher exact test and the Kolmogorov-Smirnov test were used for assessing categorical variables or continuous variables between groups. Statistical significance was set at $p < 0.05$.

ML model building and validation

Elastic net regularized logistic regression (ELR) and random forest (RF) and extreme gradient boosting (XGB) were applied to predict LNM. ELR mixes the penalties of ridge and lasso to minimize the overfitting and help variable selection. RF combines a predetermined number of decision trees (usually about 1000) generated on a random subgroup of the data set. XGB aims to improve consecutively. XGB aims to improve consecutively by creating models to explain where the previous model fails and then repeating this process (usually around 1000 times). At the same time, regularization is used to reduce overfitting. The individual models were combined to generate overall predictions. This strategy, theoretically, is advantageous when utilizing a variety of model types that represent various aspects of patients' risk profiles.

Random Over Sampling Examples (ROSE) was applied to deal with the class imbalance problem. During model creation, a 10-fold cross-validation with five repeats used for each model's hyperparameter tuning. And log loss was used as optimization metric. For ELR, the hyperparameter tuning was conducted for α and λ hyperparameters. 1000 decision trees were used to create the RF model. The split rule, minimum node size, and number of variables per tree were all hyperparameter

tuned. THE hyperparameters for the XGB model include maximum tree depth, number of optimization rounds, minimum weight in each child node, minimum loss reduction (γ), regularization penalty (η), and subsampling for regularization. These three best-performed models were then integrated to create the ensemble model (Ens) by applying logistic regression to create a linear blend of projected probabilities.

The area under the receiver operator characteristic (ROC) curve (AUC) was used to evaluate the models' discrimination power. Internal validation was carried out with 1000 resampled data sets and 0.632 bootstrapping strategy. Calibration was assessed visually and formally with the Hosmer–Lemeshow test. Isotonic regression was used to scale probabilities on the final model to enable meaningful interpretation of probability.

The VarImp function of the caret R package was used. The contribution of each variable to the global ROC curve was calculated as a percentage.

Sub-analysis

The diagnostic ability of the ML model was compared with the NCCN guidelines for LNM. In the NCCN guideline, poorly differentiated tumors, deep submucosal invasion, and lymphovascular invasion are considered predictive of LNM.

Data analysis was conducted using R version 3.5.3 (R Foundation for Statistical Computing, Vienna, Austria). The caret and caretEnsemble packages were used to train the models. The full R code to train the models is available supplementary, along with a list of packages used. The calibrated final model was designed using R Shiny (available freely at <https://predicted.shinyapps.io/Rshinyfinal/>). No data entered into the model were collected or stored.

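### The AUC is validated only by the plain 0.632 bootstrap, whose fixed 36.8% weight on the training AUC can overstate random forest and boosting

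*SAP*

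**What the plan says.** In the SAP section on ML model building and validation, three learners are fitted: "Elastic net regularized logistic regression (ELR) and random forest (RF) and extreme gradient boosting (XGB) were applied to predict LNM". The forest is large ("1000 decision trees were used to create the RF model"), and the three are then combined "by applying logistic regression to create a linear blend of projected probabilities". On performance the section states: "The area under the receiver operator characteristic (ROC) curve (AUC) was used to evaluate the models' discrimination power". The sentence after it is the only one that says how that AUC is validated: "Internal validation was carried out with 1000 resampled data sets and 0.632 bootstrapping strategy".

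The repeated 10-fold cross-validation in the same section serves hyperparameter tuning and not validation of the AUC: "And log loss was used as optimization metric". Class imbalance is handled by resampling: "Random Over Sampling Examples (ROSE) was applied to deal with the class imbalance problem". The Sub-analysis section adds: "The diagnostic ability of the ML model was compared with the NCCN guidelines for LNM".

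The SAP does not name 0.632+, an out-of-bag AUC on its own, nested cross-validation, a held-out set or an external validation set.

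**The concern.** The plain 0.632 estimator averages performance on the training patients with performance on patients left out of each bootstrap sample. Its weights are fixed whatever the degree of overfitting. That matters little for a penalised logistic model with few predictors, whose training AUC is only slightly optimistic. Random forest and boosting can fit their own training rows closely, and 36.8% of that fit goes into the reported figure.

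Three things are at stake:

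- The validated AUC of these two learners, and possibly of the ensemble, can look better than it is. A model with no predictive value can appear to have some.
- The bias differs by learner, so the ranking of the models can be distorted.
- The NCCN criteria are not fitted to these data. If the 0.632 AUC enters that comparison, the optimism falls on the model's side only.

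**Working it through.** **Inputs.** From the SAP: AUC as the measure, plain 0.632 with 1000 resamples, elastic net, random forest (1000 trees), boosting, a logistic blend, tuning on log loss, ROSE, and eight mostly binary predictors. The SAP gives no sample size, event rate, apparent AUC or validated AUC, so it has no figure to reproduce. Sample size, event rate and effects below are assumptions.

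**Weights.** The chance that a patient enters a bootstrap sample is 1 − (1 − 1/n)^n: 0.6340 at n = 100, 0.6325 at n = 500 and 0.6321 in the limit. The remaining weight is 1 − 0.632 = 0.368.

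**Formulas.**

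- Plain: AUC(0.632) = 0.368 × apparent + 0.632 × out-of-bag.
- 0.632+ with no-information AUC 0.5: R = (apparent − out-of-bag)/(apparent − 0.5), w = 0.632/(1 − 0.368R), estimate = (1 − w) × apparent + w × out-of-bag.

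**Plain 0.632 over a range of apparent AUC.**

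| Out-of-bag AUC | Apparent 0.80 | Apparent 0.90 | Apparent 1.00 | 0.632+ at apparent 1.00 |
|---|---|---|---|---|
| 0.50 | 0.610 | 0.647 | 0.684 | 0.500 |
| 0.70 | 0.737 | 0.774 | 0.810 | 0.757 |
| 0.75 | 0.768 | 0.805 | 0.842 | 0.806 |

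Example: 0.368 × 1.00 + 0.632 × 0.50 = 0.684. For 0.632+ at out-of-bag 0.70: R = 0.30/0.50 = 0.6, w = 0.632/0.7792 = 0.811, estimate = 0.189 + 0.811 × 0.70 = 0.757. The 0.632+ estimate thus still keeps 0.057 of the 0.110 excess, which is why it is proposed only as a secondary figure.

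**Simulation 1: no tuning, no ROSE, no ensemble** (n = 300 and 700; 4 data sets × 12 bootstraps; 100 trees). Without information (12% events), plain 0.632 gave 0.647 to 0.709 for the tree models against a true AUC of about 0.50. With signal (38% events) at n = 700, it gave:

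- forest with minimum leaf 1: 0.790 against true 0.665
- forest with minimum leaf 10: 0.745 against 0.702
- boosting: 0.754 against 0.682
- plain logistic regression: 0.711 against 0.716

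**Simulation 2: tuned by log loss** (n = 600; 15–17% events; 20 bootstraps; 7 replicates per cell; truth from 10,000 new patients; AUC scored on original patients; tuning done once per data set and then held fixed). Entries are apparent / out-of-bag / 0.632 / true, then the bias of 0.632. Differences of the rounded means can be 0.001 off the listed bias.

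| Setting | Random forest | Boosting | Ensemble, in-sample blend | Ensemble, out-of-fold blend |
|---|---|---|---|---|
| No information, no ROSE | 0.747/0.512/0.598/0.500, +0.098 | 0.672/0.504/0.566/0.501, +0.065 | 0.756/0.507/0.598/0.501, +0.097 | 0.548/0.504/0.520/0.498, +0.022 |
| No information, ROSE | 0.682/0.506/0.571/0.505, +0.065 | 0.661/0.514/0.568/0.502, +0.066 | 0.723/0.508/0.587/0.505, +0.082 | 0.597/0.508/0.541/0.503, +0.037 |
| Signal, no ROSE | 0.816/0.628/0.697/0.658, +0.039 | 0.730/0.635/0.670/0.665, +0.005 | 0.836/0.595/0.684/0.622, +0.061 | 0.670/0.628/0.643/0.661, −0.018 |
| Signal, ROSE | 0.766/0.616/0.671/0.650, +0.022 | 0.718/0.631/0.663/0.643, +0.020 | 0.773/0.608/0.669/0.642, +0.027 | 0.722/0.630/0.664/0.656, +0.008 |

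Standard errors are 0.01 to 0.04. Elastic net with signal was about 0. Over all learners, the out-of-bag bias was 0.00 to +0.02 without information and −0.03 to −0.01 with signal; for 0.632+ it was −0.02 to +0.03 and −0.03 to +0.01. If the apparent AUC were scored on ROSE-generated rows, random forest and boosting would be at about +0.11 without information and +0.05 to +0.06 with signal.

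**Simulation 3: tuned random forest, stronger signal** (n = 600; 16–18% events; 8 replicates per cell; original patients scored). Bias with ROSE:

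| True AUC | Plain 0.632 | Out-of-bag | 0.632+ |
|---|---|---|---|
| 0.72 | +0.045 (SE 0.006) | −0.025 | +0.018 |
| 0.84 | +0.031 (SE 0.004) | −0.005 | +0.025 |

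Without information, plain 0.632 was biased by about +0.08. Both alternatives had the lower root mean squared error in every cell.

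**The case against.** The no-information case is a stress test and does not describe this study. The inputs include the features that, by the SAP's own Sub-analysis section, the NCCN guideline treats as predictive. The clearest biases come from that case. The bounds of 0.684 and 0.810 need an apparent AUC of 1.00, whereas the tuned runs reached only 0.55 to 0.84.

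Under signal with ROSE, which is what the SAP specifies, simulation 2 shows 0.008 to 0.027 with wide standard errors. There, plain 0.632 lies nearer the truth than out-of-bag in 3 of the 4 tree and ensemble cells (mean absolute error about 0.019 against 0.027), and in 5 of 8 signal cells with and without ROSE. The blend may be settled by the supplementary R code, and nothing says that the 0.632 AUC is what is compared with NCCN.

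Much of this stands as a limit on size: the bounds are only bounds, and the ensemble and NCCN effects are conditional. The argument that out-of-bag does no better with signal does not stand for random forest. With stronger signal and tighter standard errors (simulation 3), plain 0.632 was clearly optimistic, and out-of-bag and 0.632+ both had lower error. For boosting and the ensemble under signal, neither estimator is shown to be more accurate.

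**Conclusion.** The concern holds and should be fixed. The SAP relies on one fixed-weight estimator that can overstate the AUC of flexible learners, and tuning and ROSE reduce this without removing it. With tuning and ROSE, the bias for random forest was +0.022 to +0.045 with signal and +0.065 to about +0.08 without. For boosting it was +0.066 without information and an uncertain +0.020 with signal. Elastic net is little affected when there is signal. The ensemble is exposed if the blend is fitted on in-sample probabilities (+0.082 without information, +0.027 with signal, both with ROSE); with an out-of-fold blend the bias is within noise.

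The direction follows from the estimator. The sizes rest on an assumed 600 patients, 15–18% events, assumed effects and few replicates, so confidence in them is medium.

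**What to change.** - Report the out-of-bag bootstrap AUC, or a nested cross-validated AUC, as the internal-validation figure in place of plain 0.632. Give 0.632+ (no-information AUC 0.5) beside it as a secondary estimate.
- Repeat ROSE, tuning, blending and isotonic scaling inside every resample, and score the AUC on original patients and not on ROSE-generated rows.
- State whether the blend is fitted on out-of-fold probabilities.
- Use the same out-of-bag predictions in any comparison with the NCCN criteria.

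No new data are needed. The cost is SAP wording and computing time. Ten folds with five repeats are 50 fits per tuning candidate, so 1000 resamples mean 50,000 fits per candidate and learner; 200 resamples would be acceptable and bring this to 10,000. The reported AUC becomes less favourable. The out-of-bag figure is somewhat conservative when there is signal (about 0.01 to 0.03 low in simulation 2), which is the reason to show 0.632+ with it.

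### The only formal calibration measure is a Hosmer-Lemeshow p-value, which estimates neither the size nor the direction of any error in the released risks

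*SAP*

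**What the plan says.** In *ML model building and validation* the SAP gives one sentence on how calibration is judged: "Calibration was assessed visually and formally with the Hosmer–Lemeshow test". It does not state the number of groups, the degrees of freedom, which predictions are tested, or what follows from either result.

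Four other statements bear on the point:

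- Training data are rebalanced: "Random Over Sampling Examples (ROSE) was applied to deal with the class imbalance problem".
- Validation is by resampling: "Internal validation was carried out with 1000 resampled data sets and 0.632 bootstrapping strategy". The calibration test is not tied to this step.
- Probabilities are then rescaled: "Isotonic regression was used to scale probabilities on the final model to enable meaningful interpretation of probability". The SAP does not say whether the test comes before or after this.
- The result is released for use: "The calibrated final model was designed using R Shiny", in a freely available online tool.

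The only significance threshold, p < 0.05, appears in *Predictor characteristics* ("Statistical significance was set at"), directly after the between-group comparisons.

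**The concern.** The null hypothesis of the Hosmer-Lemeshow test is that the model is well calibrated, so the favourable result is non-significance. With few LNM cases that result is easy to obtain whether or not the risks are right. With many cases a small error can be flagged. Either way, the p-value does not say whether risks are too high, too low or too extreme, or by how much.

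Training on rebalanced classes can move predicted risks away from the true LNM frequency, and the isotonic step is there to restore their meaning. A user of the calculator reads an individual probability, so what needs reporting is how far off the probabilities may be, with its uncertainty. The planned formal measure cannot supply that.

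**Working it through.** **Inputs.** The SAP gives no sample size, LNM frequency, group count or error rate for the test, so there is no stated figure to reproduce. Assumed: ten equal-sized groups, n from 200 to 1000, LNM from 10% to 25%, and a normally distributed linear predictor (SD about 1.0 to 1.6).

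**Statistic.** H = Σ (O − E)² / [E(1 − E/m)], summed over g groups of size m, where O and E are observed and expected LNM cases in the group.

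**Reference distribution.** For a logistic model tested in its own fitting data, the usual reference is chi-square on g − 2 df. For predictions not fitted to the tested patients it is g df. With g = 10 the 5% cut-offs are 15.51 (8 df) and 18.31 (10 df).

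**1. Detection on 10 df, LNM 13%** (simulated; n = 300 / 600 / 1000)

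| Error in stated risk | Hosmer-Lemeshow | Joint intercept-and-slope test |
|---|---|---|
| 0.75 of the truth | 36 / 58 / 76% | 39 / 69 / 89% |
| One third too high | 14 / 48 / 77% | 58 / 89 / 98% |

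Repeat simulations with somewhat different risk distributions gave 33–36 / 55–58 / 76–78% in the first Hosmer-Lemeshow cell and 14–19 / 43–55 / 77–86% in the second. Subtracting from 100%, the test misses the first error about 65 / 42 / 23% of the time and the second about 85 / 50 / 20%.

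**2. Dependence on unstated inputs.** At 20% LNM and n = 1000, both tests detect both errors about 95% of the time or more. On the 8-df cut-off with SD 1.0, pass rates run from 93% (n = 200, LNM 10%, risks 25% too high) to about 0% (n = 1000, LNM 20%, risks 33% too high).

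**3. False rejection, conditional.** If the test is run on predictions not fitted to the tested patients, with ten groups and the usual 8 df, P(chi-square on 10 df > 15.507) = 0.1146. A perfectly calibrated model is then rejected 11.5% of the time instead of 5%. With other group counts the figure is 16.7% (5 groups), 12.7% (8), 9.9% (15) and 9.0% (20).

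This does not go with the detection rates in step 1. The matching 8-df rates at 13% LNM are 48 / 69 / 85% for risks at 0.75 of the truth and 29 / 64 / 90% for risks one third too high. On 10 df, false rejection at 13% LNM is about 4–6%.

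**4. What an estimate would show.** Approximate 95% limits for the observed/expected ratio are the ratio multiplied and divided by exp{1.96 √[(1 − π)/(nπ)]}, where π is the LNM proportion. With π = 0.13:

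- n = 300: exp(1.96 × √(0.87/39)) = 1.34
- n = 600: exp(1.96 × √(0.87/78)) = 1.23
- n = 1000: exp(1.96 × √(0.87/130)) = 1.17

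Risks one third too high give a ratio of 1/1.333 = 0.75. At n = 600 the limits would be 0.75/1.23 = 0.61 to 0.75 × 1.23 = 0.92, which shows both direction and plausible size. At n = 300 they would be 0.56 to about 1.00. That is barely conclusive, but it shows how large an error remains possible; a non-significant p-value does not.

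**The case against.** - **The visual check.** Calibration is also assessed visually, and a calibration plot shows direction and rough size. This stands: the lack of size and direction belongs to the formal test, not to the whole assessment. A plot alone still gives no summary estimate or interval.
- **A pass/fail rule.** A reader might infer that the SAP treats p ≥ 0.05 as proof of calibration. It does not say so. The threshold sits in another section and no decision is attached to the test.
- **Frequent passing.** A reader might infer that the test will often pass risks wrong by a quarter to a third. That depends on a sample size and LNM frequency the SAP does not give. It is true for a few hundred patients or low LNM frequency, and false at n = 1000 with 20% LNM.
- **The 11.5%.** A reader might add this to the miss rates above. The two rest on different degrees of freedom, and the SAP fixes neither the df nor the prediction set.
- **Ties.** Isotonic scaling produces tied risks, which make ten equal groups awkward. The SAP does not say the test is applied after scaling, and the test is mentioned first, so this is an unspecified detail and not an error.
- **The alternative test.** Its advantage is small for risks at 0.75 of the truth at n = 300 (39% against 36%). For a calibration slope of 0.8 it varied with the simulated risk distribution: 32 / 58 / 81% against 19 / 32 / 52% in one, 21 / 41 / 60% against 21 / 28 / 41% in another. Only simple shifts and slopes were simulated; a grouped test might do better against irregular miscalibration. This stands as a reason to keep Hosmer-Lemeshow as an option.

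**Conclusion.** The point holds in a limited form. The one formal calibration measure yields no estimate, direction or interval, and its result reflects the number of LNM cases as well as the size of the error. The miss rates of about 65 / 42 / 23% and 85 / 50 / 20% rest on assumed values (13% LNM, ten groups, 10 df, a normal linear predictor) and are illustrations, not properties of this study. The 11.5% false-rejection rate is exact but applies only to unfitted predictions, ten groups and 8 df.

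The case for change does not depend on any of these figures. Intervals for intercept, slope and observed/expected ratio are informative at any sample size, and the released probabilities need them. The planned discrimination results are unaffected. Label: cheap improvement.

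**What to change.** In *ML model building and validation*, replace the calibration sentence with wording such as: *Calibration will be reported as the calibration intercept, calibration slope and observed/expected ratio, each with a 95% confidence interval, on the optimism-corrected (out-of-bag) predictions, with a smoothed calibration curve as the visual check. A non-significant p-value will not be read as evidence of calibration.*

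State whether these predictions are taken before or after isotonic scaling. If after, say how scaled risks of exactly 0 or 1 are handled, since their logit is undefined. The Hosmer-Lemeshow test may remain as a secondary item if its number of groups, degrees of freedom and prediction set are given.

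The cost is a change of wording and one extra logistic fit of LNM on the logit of predicted risk. The small downside is that reported calibration may look less favourable than a non-significant p-value.

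### The released isotonic-scaled risks are not tied to a calibration check outside the fitting patients, and isotonic regression can show a lymph node metastasis risk of exactly 0%

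*SAP*

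**What the plan says.** All of this stands in the SAP under *ML model building and validation*, except the release, which is in the software paragraph at the end of *Sub-analysis*.

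- Class balancing: "Random Over Sampling Examples (ROSE) was applied to deal with the class imbalance problem".
- Tuning: "a 10-fold cross-validation with five repeats used for each" model. Cross-validation is tied to tuning only.
- Ensemble: the three models are combined "by applying logistic regression to create a linear blend of projected probabilities". The data used to fit this blend are not named.
- Validation: "Internal validation was carried out with 1000 resampled data sets and 0.632 bootstrapping strategy". The sentence names neither calibration nor scaling.
- Calibration: "Calibration was assessed visually and formally with the Hosmer–Lemeshow test".
- Scaling, in the next sentence: "Isotonic regression was used to scale probabilities on the final model to enable meaningful interpretation of probability".
- Release: "The calibrated final model was designed using R Shiny".

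The text does not say which patients the isotonic map is fitted on, whether the calibration check comes before or after scaling, whether the resamples repeat the scaling, or whether the output is bounded. The full R code is said to be supplementary. It is not among the documents at hand.

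**The concern.** The scaled probability is the end product, because it is the number a user of the calculator reads. Two questions follow.

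First, does the planned calibration evidence describe that number in patients who did not shape the isotonic map? If not, a good plot and a non-significant test give reassurance that was never earned.

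Second, isotonic regression outputs observed event rates of blocks of patients. The lowest block often has no events, so its output is exactly 0, and the top block can be exactly 1. A displayed 0% is a statement of certainty that a finite block cannot support, and some of the patients who receive it will have LNM.

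**Working it through.** **Inputs.** From the SAP: isotonic scaling, plot plus Hosmer–Lemeshow, 1000 resamples with 0.632 weighting, 10 folds × 5 repeats. The SAP gives no sample size, LNM rate, AUC or calibration result, so there is no figure to reproduce. Sizes below rest on assumed n, LNM rate and AUC.

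**Step 1. The possible readings.**

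| Reading | Does it validate the released risks? |
|---|---|
| Test before scaling | No. It concerns other probabilities. |
| Test after scaling, in the fitting patients | No. It is nearly automatic (step 2). |
| Calibration under resampling, scaling refitted each time | Yes, but the text does not commit to it. |

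**Step 2. Why the in-sample check is nearly automatic.** A block with n_b patients and d_b events gets p_b = d_b/n_b, so Σ(y − p) = 0 within each block. Summing over blocks gives Σ(y − p) = 0 and Σp(y − p) = 0. These are the least-squares equations for y on p with intercept 0 and slope 1. They hold for any score, provided the fit is not constant.

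The simulation used a single score, n = 300, 600 and 1200, LNM 10% and 20%, and 300 runs per cell (6 × 300 = 1,800 data sets per AUC).

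- In-sample linear slope: 1.0000 in every cell.
- Hosmer–Lemeshow grouped on scaled risk: 0 of 1,800 rejections for a worthless score (AUC 0.50, slope 0.00 in new patients) and 0 of 1,800 at AUC 0.80. With ties split by raw score it rejected in 1–10%.
- A separate simulation (n 200–1000, AUC about 0.75–0.84) gave p > 0.05 in 98.5–100% of runs in the fitting data, but in 30–49% in new data. There, a new LNM case in a group with all-zero predictions counted as failure.

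**Step 3. Exact zeros.** Everyone below the lowest-scoring LNM-positive patient in the fit lies in event-free territory and gets 0. If a new LNM-positive score is exchangeable with the m in the fit, it is the lowest of the m + 1 with probability 1/(m+1). The true LNM rate among those shown 0% is LNM rate × share of positives shown 0% ÷ share of all shown 0%. For the first row below: 0.10 × 0.0296 / 0.193 = 1.5%.

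| n, LNM rate (AUC 0.80) | m | 1/(m+1) | LNM-positive shown 0%, simulated | All new patients shown 0% | True LNM rate among them |
|---|---|---|---|---|---|
| 300, 10% | 30 | 3.23% | 2.96% | 19.3% | 1.5% |
| 300, 20% | 60 | 1.64% | 1.57% | 12.0% | 2.6% |
| 600, 10% | 60 | 1.64% | 1.57% | 13.3% | 1.2% |
| 600, 20% | 120 | 0.83% | 0.85% | 8.3% | 2.1% |
| 1200, 10% | 120 | 0.83% | 0.85% | 9.2% | 0.9% |
| 1200, 20% | 240 | 0.41% | 0.43% | 5.4% | 1.6% |

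The separate simulation, which interpolated between fitted points, had an exact-zero block in at least 99% of fits in every setting and showed 0% to 3.5–31.9% of new patients.

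**Step 4. What a zero block supports.** With 0 events in a block of b patients, the one-sided 95% upper limit is 1 − 0.05^(1/b): 13.9% at b = 20, 5.8% at 50, 3.0% at 100 and 1.5% at 200. These limits are nominal, because the data choose where the block ends.

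**Step 5. Does in-sample fitting matter for the zeros?** In a simulated blend of three untuned learners (about 13% LNM, 60 runs per size), the share of LNM-positive patients shown 0% at n = 600 / 300 was 2.4% / 7.3% with an in-sample isotonic fit and 0.9% / 3.3% with an out-of-fold fit. In-sample scores break exchangeability in the unfavourable direction.

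**Step 6. Would the bootstrap reading work?** Linear slopes at AUC 0.80, in the row order above; the 0.632 value is 0.632 × out-of-bag + 0.368 × 1.

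| | 1 | 2 | 3 | 4 | 5 | 6 |
|---|---|---|---|---|---|---|
| Out-of-bag | 0.67 | 0.79 | 0.76 | 0.85 | 0.83 | 0.90 |
| 0.632-weighted | 0.79 | 0.87 | 0.85 | 0.91 | 0.89 | 0.94 |
| New patients | 0.81 | 0.87 | 0.86 | 0.90 | 0.90 | 0.94 |

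The 0.632 value is within 0.02 of the new-patient slope in every cell, and out-of-bag is 0.04–0.14 too low. For a worthless score it is the other way round: the weighted logit slope (risks truncated at 1–99% for the computation) was 0.26–0.33 against −0.17 to −0.07 out-of-bag. Neither value alone is enough.

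**The case against.** The strongest reply is that this rests on silence. The SAP does not say that the map is unbounded or fitted in-sample, and the supplementary code may settle both. The calibration sentence directly follows the bootstrap sentence, so calibration under resampling is a natural reading, and step 6 shows that it would work well. These points stand in part. A reader might infer that the calibration check was done in-sample, or that the calculator does display 0%. The documents show neither. What remains is that the text does not commit to the one valid reading, and that exact zeros are a property of isotonic regression as named, since a bound would be an addition to it. Step 6 also uses a single score, without overfitting by the base learners, and needs the scaling refitted in each resample.

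A second reply is that the average error is small. That also stands: Brier scores differed by only 0.002–0.004 between recalibration methods. The problem lies in the validation and in the extremes.

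A reader might also infer that ROSE leaves the released risks inflated, or that recalibrating was a mistake. Neither follows. If the blend is fitted on balanced data, some rescaling is needed, and an isotonic fit on real patients restores the mean whichever data the blend used.

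**Conclusion.** The point holds and should be fixed. As written, the SAP does not ensure valid calibration evidence for the risks it releases, and its scaling method can give exact 0% risks to patients who have LNM. The in-sample slope of 1 and intercept of 0 are algebra and need no assumption beyond a non-constant fit. The 1/(m+1) share needs exchangeable scores and a step function; ties or interpolation would change it somewhat. All other sizes are illustrative, because n, LNM rate and AUC are assumed, and the blend figures come from untuned learners where the SAP specifies tuning. Confidence is medium, since the unseen code could resolve both parts.

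**What to change.** - Fit the recalibration on out-of-fold ensemble predictions of the real (non-ROSE) patients, and say so. State also which data the logistic blend is fitted on.
- Refit the recalibration within each planned bootstrap resample, keeping copies of one patient in the same fold.
- Report the calibration plot, intercept and slope of the released risks from that resampling, with both out-of-bag and 0.632-weighted values, in place of relying on the Hosmer–Lemeshow p-value. State the scale of the slope: a logit slope is undefined at 0 and moves with any truncation.
- Prevent displayed risks of exactly 0 or 1, either by a pre-stated bound based on the size of the end block (for example its binomial upper limit) or by logistic recalibration.

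**Cost.** SAP wording, a code change and a calculator update. Computing time is the main burden if tuning is repeated: 10 × 5 = 50 fits per candidate setting per resample, so 50 × 1000 = 50,000 per setting per learner, multiplied by the grid size. Two values for each of the six XGB hyperparameters make 2⁶ = 64 settings, or 3.2 million fits on a full grid. A single tenfold run cuts the 50,000 to 10,000, and holding tuned values fixed cuts it further, at the price of not validating the tuning. The other downsides are a bound that must be stated, or a less flexible curve under logistic recalibration, and an out-of-bag slope that is somewhat pessimistic because each resample holds about 63% of the patients.
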